- **Specify objectives and hypotheses to be tested in the research project**

Aim 1: Pilot test, in a randomized controlled design (N=120, 60 in each group), the effect of *ED GOAL* administered by trained nurses on patient and caregiver ACP engagement one month after leaving the ED.

Hypotheses: ACP engagement (a composite outcome combining patient-reported and EMR outcomes) will significantly increase in those who received *ED GOAL* compared to usual care.

Aim 2: Identify the patient-perceived benefits and obstacles of ACP conversations after *ED GOAL* using semi-structured interviews (N~30).

[figure not shown]
Rationale: Most patients who underwent our intervention in prior studies expressed their gratitude and reported how helpful the intervention was in their lives. Yet, these perceived benefits (“opened my eyes about what I need to focus in my life”) may be difficult to capture using validated, quantitative instruments. Furthermore, we will also elicit patient-perceived barriers to completing the ACP conversations.

3. General Description of Study Design

- **Explain the basic study design, e.g., parallel group, randomized controlled trial, open-label single arm study, cross over, adaptive, etc.**

This is a two-armed, parallel-design, pre-/post-intervention assessment study. We will conduct a randomized controlled trial for *ED GOAL* on a cohort of 120 older adults with serious illness to collect patient-centered outcomes and determine preliminary efficacy on increasing ACP engagement (self-reported and/or in the electronic medical record) one month after leaving the ED. We will also conduct qualitative interviews with participants of *ED GOAL*.

- **Provide study schema as applicable (a schema is required for greater than minimal risk studies, and optional for minimal risk studies)**

4. Subject Selection

Describe sources of subjects and procedures for subject selection, including the following:

- **Inclusion/Exclusion Criteria**

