6. STUDY PROCEDURES

Provide detailed description of all study visits, procedures, and data collections, including:

- **Description of each study visit and procedures at each visit (include a schedule/table of study procedures)**

Initial enrollment (~30 to 60 minutes total):

After the consent, our trained study clinician will administer the intervention to the participant in-person, on the phone, or over zoom depending on participant preference. After the intervention is completed, the RA will obtain post-enrollment questionnaires and also schedule dates/times for the follow-up appointments. With participants' permission, the study clinician will document the clinically important findings elicited from the participant (e.g., preferences for end-of-life care goals) in Epic's ACP module and also send an email regarding the findings to patient's outpatient clinicians within Mass General Brigham health system via secure email. The study team will also provide the post-enrollment patient handout (see attachment) to the participants. All participants in the intervention arm will receive the same intervention and follow-up procedures.

Follow-up appointments (~30 to 45 minutes each):

During the scheduled follow-up appointments on the phone/zoom, our RA will administer surveys to assess for the outcomes. In addition, if the participants report that they have not had conversations with their outpatient clinicians about ACP, our study clinician will conduct brief coaching to overcome the obstacles participants might be facing in this process and also document clinically relevant information in Epic to notify to the outpatient clinician.

Table 3 Study visits		
Study visit	Intervention	Outcome assessment
Initial enrollment	ED GOAL	Post-enrollment survey

1-month follow-up	ACP navigation coaching (as needed)	Follow-up patient-reported outcomes surveys
3-month follow-up	ACP navigation coaching (as needed)	Follow-up patient-reported outcomes surveys
6-month follow-up	ACP navigation coaching (as needed)	Follow-up patient-reported outcomes surveys

- **Description of study drugs, devices, or other interventions/exposures administered, including:**

- **Dose, method of administration, schedule of administration, dose modifications**

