EMR documentation (primary outcome)	Review EMR to see if new documentation of ACP conversation, change in code status, or advance directive forms documented by physicians or mid-level providers exist.	Baseline & at 1, 6, and 12 months
Self-reported ACP conversation survey (primary outcome)	Quantitative and qualitative questionnaires to assess the self-reported completion of ACP conversations with outpatient clinicians and families as well as barriers/facilitators of this process.	At 1, 3, and 6 months

Heard and understood survey (secondary outcome)	A validated instrument for seriously ill patients to report how well they feel heard and understood about their wishes for end-of-life care. ³¹	Baseline & 1, 3, and 6 months
Quality of communication survey (secondary outcome)	A validated instrument to measure the quality of communication about end-of-life care. ³²	Baseline & at 1, 3, and 6 months
Healthcare utilization (secondary outcomes)	Review EMR to see # of urgent care visits, ED visits, hospitalizations, hospice visits, and outpatient visits.	At 6 and 12 months before and 1, 6, 12 months after enrollment
Mortality	Review EMR to determine patient's vital status.	At 1, 3, and 6 months
Qualitative benefits and obstacles of ACP conversations after ED GOAL (secondary outcome)	Semi-structured interviews to assess the benefits of ED GOAL and obstacles participants faced in completing more ACP conversations with their outpatient clinicians and loved ones after ED GOAL (see interview guide).	At 1, 3, and/or 6 months

- **Description of planned genetic research as applicable (e.g., specific description of whole genome sequencing, creation of immortalized cell lines or induced pluripotent stems cells, and sharing of genetic material with collaborators and central repositories as applicable, etc.)**
Not applicable.
- **Description of plans for return of research results as applicable (e.g., specific description of, rationale for, and process by which research results will be returned, including to whom, by whom, and when, etc.). Include plans for managing incidental findings as applicable.**
Not applicable.
- **Definition of primary and secondary outcomes/endpoints. Note that outcome measures should be quantifiable and measurable.**
Please see **Table 4** above.
- **Definition of study termination criteria, e.g., objective criteria for clinical worsening, lack of improvement, and/or unacceptable adverse events**

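### The EMR outcome limits authors by profession but does not exclude the study team's own Epic notes, so notes written as part of ED GOAL may count towards the endpoint

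*Combined protocol and SAP*

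**What the plan says.** **What the study team writes.** Section 6, Initial enrollment: once ED GOAL has been given, and if the participant permits, "the study clinician will document the clinically important findings elicited from the participant". The entry goes into Epic's ACP module, and end-of-life care preferences are the example given. Section 6, Follow-up appointments: when a participant reports no ACP conversation with an outpatient clinician, the study clinician coaches and will "document clinically relevant information in Epic to notify to the outpatient clinician". Table 3 places this coaching at 1, 3 and 6 months.

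**What the outcome counts.** The EMR row of the measures table in section 6 reads: "Review EMR to see if new documentation of ACP conversation, change in code status, or advance directive forms documented by physicians or mid-level providers exist". Reviews take place at "Baseline & at 1, 6, and 12 months". Neither this row nor section 9 has a rule on entries written by study staff.

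**Who delivers ED GOAL.** Aim 1 in section 2 concerns the effect of ED GOAL "administered by trained nurses on patient and caregiver ACP engagement one month after leaving the ED". Sections 5 and 6 speak of the study clinician and give no licence type.

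**What role the outcome has.** The Aim 1 hypothesis treats ACP engagement as "a composite outcome combining patient-reported and EMR outcomes". The measures table labels EMR documentation a primary outcome. Section 9 names self-reported engagement as primary and discusses ACP documentation as the secondary outcome.

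**The concern.** The intervention writes into the record from which the outcome is read. Section 1 describes ED GOAL as a way to get patients to take up ACP with their outpatient clinicians. A note by the study clinician shows that the study visit took place, not that an outside clinician documented anything. If such notes count, a difference between arms can arise from study charting alone.

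The coaching note has a further feature: it is triggered by a report that no outpatient conversation has occurred. If counted, it could turn a self-reported failure into an EMR success at a later review.

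The pilot's stated purpose is to estimate preliminary effect sizes for a larger multi-site trial. An inflated documentation difference would carry into that design.

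**Working it through.** **Step 1. Can a study note meet the definition?** There are two open questions, and the text settles neither.

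| Author limit applies to | Study clinicians are registered nurses | Some are nurse practitioners, physician assistants or physicians |
|---|---|---|
| All three kinds of entry | Notes excluded | Their notes can count |
| Advance directive forms only | ACP conversation notes can count | ACP conversation notes can count |

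In one of the four cells the existing wording already solves the problem. In the other three it does not.

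**Step 2. Which reviews are exposed?** The enrolment note precedes the 1-month review and could affect it and the later ones. Coaching starts at the 1-month contact, so coaching notes mainly affect the 6- and 12-month reviews. Whether a coaching note would qualify as documentation of an ACP conversation is itself unclear.

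**Step 3. How large could the effect be?** The plan gives no figure on this point, so there is none to reproduce.

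- From the documents: 60 per arm (section 2); 0.05 threshold (section 9); two-sided Fisher's exact test (section 9, power paragraph).
- Assumed: p0, the rate of outside documentation in both arms, and q, the share of intervention participants with a study note that counts. The documents give neither. Study notes are taken to be independent of outside documentation, and controls are taken to have none.

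With no effect on outside clinicians, the intervention rate is p1 = p0 + (1 − p0) × q, so the spurious difference is (1 − p0) × q. The chance of significance is the sum, over all pairs of counts, of Binomial(60, p1) × Binomial(60, p0) for the pairs with Fisher p ≤ 0.05.

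For p0 = 20%:

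| q | Intervention rate | Spurious difference | Chance of p ≤ 0.05 |
|---|---|---|---|
| 0 | 20% | 0 | 2.8% |
| 10% | 0.20 + 0.80 × 0.10 = 28% | 8 points | 12.4% |
| 20% | 0.20 + 0.80 × 0.20 = 36% | 16 points | 42.0% |
| 25% | 0.20 + 0.80 × 0.25 = 40% | 20 points | 60.0% |

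As a single example of the last row, 24/60 against 12/60 gives Fisher p = 0.028.

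**Step 4. Sensitivity.** As p0 goes from 5% to 40%, the chance of significance runs from 1.1% to 3.2% at q = 0, from 29.7% down to 7.5% at q = 10%, from 81.1% down to 21.5% at q = 20%, and from 93.4% down to 32.3% at q = 25%. With 54 per arm (60 less the 10% deaths that section 9 expects) and p0 = 20%, the four rows become 2.7%, 11.3%, 37.7% and 54.9%.

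**The case against.** The strongest reply is that a filter already exists. The outcome names physicians or mid-level providers, and Aim 1 says nurses deliver ED GOAL. If they are registered nurses and the limit covers every kind of entry, q is zero and nothing is inflated. This stands as a real possibility. It does not settle the matter, because it needs two facts that the plan does not state. A limit by profession is also not a limit by study role.

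Other points narrow the concern:

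- The enrolment note needs permission, so not every participant will have one. This stands, but step 3 shows that a counted share of 10% to 25% is enough to matter.
- The pilot is described as not powered for significance, the only EMR test named in the analysis text is a within-arm binomial test, and Fisher's test appears only in the power paragraph. This stands: the Fisher probabilities are a yardstick, and the spurious difference in points is the more relevant quantity.
- Conversations with clinicians and families are also measured by a separate self-report survey, which study charting does not fill. This stands and limits the damage to the EMR outcome and any composite that uses it.
- Follow-up of the control arm is not described. That only the intervention arm receives study notes is inferred from the enrolment text and Table 3. If controls also had coaching notes, the between-arm inflation would differ, and those notes would need excluding too.

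A reader might infer that the principal investigator, as backup, will write ACP notes and so pass the author limit. Section 6 offers that backup only for equivocal delirium and cognition assessments, so it does not support the inference.

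**Conclusion.** The gap is real: the definition limits authors by profession and does not exclude study-team entries, while the intervention calls for such entries. Whether any of them would count depends on the study clinicians' licence type and on how far the author phrase reaches. A reader might infer that the intervention certainly generates its own endpoint, or that the trial's main conclusion is compromised. The documents support neither. Contamination is possible but not shown, and its weight depends on whether the EMR outcome is a composite component, primary or secondary, on which sections 2, 6 and 9 disagree.

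The size is conditional. With no true effect, 60 per arm and an assumed 20% base rate, the spurious difference is 0, 8, 16 or 20 points, and the chance of a significant Fisher result is 3%, 12%, 42% or 60%, when 0, 10%, 20% or 25% of intervention participants have a counted note. The zero case is as compatible with the text as the others. The outcome definition should be changed, because small leakage is enough to mislead and the remedy is cheap.

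**What to change.** Add to the EMR outcome definition in section 6: *Entries authored by, or on behalf of, any study clinician or study staff member, including enrolment and coaching notes, do not count.* Abstract the author, professional role and date of each qualifying entry, and apply the rule to both arms at 1, 6 and 12 months. When making the edit, state the EMR outcome's role consistently in sections 2, 6 and 9.

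The cost is one sentence and a small addition to the abstraction form. No clinical procedure changes: study clinicians can chart as planned. The intervention-arm rate may look lower than it would with study notes counted. If those notes were never meant to count, the change only records that intention.

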*NYHA Stage III/IV congestive heart failure, chronic obstructive lung disease on home oxygen, chronic kidney disease on dialysis, or metastatic solid tumor cancer. In addition, patients with NYHA Stage I/II congestive heart failure, chronic obstructive lung disease not on home oxygen, chronic kidney disease not on dialysis will be included if recent hospitalization in the last 12 months exists.	**e.g., MOLST, medical order for life-sustaining treatment, documented serious illness conversations in clinician notes within the last 3 months, etc.

• **Local Recruitment Procedures:**

Explain in detail the methods and procedures you will use to recruit participants. Describe in a step-by-step procedure below:

- **How individuals are identified for recruitment including description of use of recruitment materials such as flyers, brochures, advertisements, letters, etc.**

Our research team will review the medical records in Epic to identify the potential subjects to approach in this study. To identify potential subjects in the ED, we will review the ED patient lists Monday to Friday between 8am to 6pm. To capture potential subjects we missed during this screening period, we will also review medical records of patients who visited the ED in the last 10 days so that we can enroll them virtually after leaving the ED/hospital (if admitted).

- **Who is responsible (role on research team) for identifying and recruiting individuals**

Trained RAs will search through the medical records to find potential subjects meeting our inclusion and exclusion criteria. The study clinician consenting the subjects will double check the eligibility criteria prior to consent.

- **When individuals are recruited**

Subjects will be approached for recruitment at the time of ED visit, during their hospitalization after the ED visit, or within 10 days of leaving the ED.

- **Where individuals are recruited**

We will recruit subjects in the ED, ED observation unit, or hospital floor at Brigham and Women’s Hospital, Massachusetts General Hospital, and Brigham and Women’s Faulkner Hospital.

We will make every attempt to enroll/approach the patient in the ED. We will follow the following steps:

1. When potential subjects are identified in the ED, clinical appropriateness is assessed with the treating clinicians;
2. The treating clinicians will introduce the study and obtain permission for our research team to approach the subject in the ED; and

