Upon classification of eligible participants into the correct group above, we will randomly assign them into one of two arms of the study using block randomization of four using a computer-generated algorithm:

- 1) Intervention (*ED GOAL*)
- 2) Control (usual care)

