Our intervention is followed by scheduled, follow-up visits at one, three, and six months afterwards. The follow-up visits will be performed to assess the outcomes as well as to serve as the ACP care navigation/coaching by our study clinician.

Study clinician training:

We will train the study clinicians to administer these tools by 3-hour didactic on the concepts of delirium, cognitive impairment, and dementia, as well as bedside practice administration with the PI until competency is demonstrated (PI will self-record the responses next to the study clinician administering the instrument and compare the results. We will repeat this process with new patient volunteers until there is no discrepancy). In the case of equivocal findings on these assessments administered by study clinician, the PI backup will be available.

Intervention fidelity:

To ensure that all study clinicians deliver our intervention consistently, we will check the intervention fidelity. The percent adherence to the intervention fidelity checklist will be measured for every participant encounter (see attached fidelity checklist). High fidelity will be defined as mean adherence of >70% to the components on the fidelity checklist, which is consistent with expert consensus for behavioral intervention studies.²⁸

- **Justification and safety information if FDA approved drugs will be administered for non-FDA approved indications (“off-label”): How are doses, routes of administration, or participant populations different from FDA approved indicated use?**

Not applicable.

- **Description of specific data variables to be collected, including data collection methods, assessments, data collection sheets, and/or schedule of assessments (A schedule/table of study assessments is preferred)**

Measures	Descriptions	Timing
ACP engagement survey for patients (primary outcome)	Used for patients , this validated instrument will measure the self-reported processes for ACP (knowledge, contemplation, self-efficacy, and readiness), and ACP behavior. ²⁹	Baseline & at 1, 3, and 6 months
ACP engagement survey for caregivers (primary outcome)	Used for surrogate decision-makers , this ACP engagement survey is validated to measure the same ACP processes and behaviors. ³⁰	Baseline & at 1, 3, and 6 months

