Describe plans for statistical analysis, including:

- **Statistical methods/data analysis plan**

Aim 1 quantitative data analysis:

We will conduct an intention-to-treat analysis. Since the primary outcome is mean change in self-reported ACP engagement, we do not expect differences among patients who are admitted vs. discharged. For our secondary outcome, we suspect that there is a propensity of more ACP documentation in patients who are hospitalized and missingness in patients who are primarily cared for at outside institutions. We will plan to use regression in subgroup analysis for ACP documentation to account for hospitalization status. In addition, we will perform sensitivity analyses to account for clustering by individual outpatient clinicians, palliative care consultations, and cognitive impairment status. We will also perform sensitivity analyses for survey respondents (e.g., patients vs. caregivers). We will compare patient demographics by study arm to assess randomization using bivariable analyses (t-test for continuous variables and chi-square for categorical variables). The mean changes in ACP engagement (primary outcome) at one month will be compared by study arms to estimate effect sizes. Within arms, we will use a one-sample binomial exact test of proportions for categorical outcomes (e.g., EMR documentation), and Wilcoxon signed ranks test for ordinal outcomes (e.g., ACP Engagement Survey) at baseline, after the intervention at one month. A p-value of 0.05 will be the significance threshold. To address missing data, I will conduct a secondary analysis using linear mixed models at baseline and one month. For qualitative outcomes,

Aim 2 qualitative data analysis:

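### Nothing in the protocol prevents the assessor of the one-month outcomes from knowing the participant's arm

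*Combined protocol and SAP*

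**What the plan says.** Section 6 (Study Procedures, Initial enrollment) has the study clinician deliver ED GOAL and then brings in the RA: "After the intervention is completed, the RA will obtain post-enrollment questionnaires and also schedule dates/times for the follow-up appointments". Under Follow-up appointments it continues: "During the scheduled follow-up appointments on the phone/zoom, our RA will administer surveys to assess for the outcomes". If the participant reports no ACP conversation with an outpatient clinician, "our study clinician will conduct brief coaching to overcome the obstacles participants might be facing in this process". The intervention description in Section 6 gives these contacts two jobs: "The follow-up visits will be performed to assess the outcomes as well as to serve as the ACP care navigation/coaching by our study clinician". Table 3 lists the coaching in its Intervention column.

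The measures table in Section 6 labels four measures as primary: the ACP engagement surveys for patients and for caregivers, the self-reported ACP conversation survey, and EMR documentation. The last is described as "Review EMR to see if new documentation of ACP conversation, change in code status, or advance directive forms" recorded by physicians or mid-level providers. Section 9 (Aim 1 quantitative data analysis) names one primary measure, "Since the primary outcome is mean change in self-reported ACP engagement", compared between arms at one month, and discusses ACP documentation as secondary.

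The comparator in Section 5 is usual care, with no attention or sham contact described. No section mentions masking of RAs, EMR abstractors or analysts.

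**The concern.** Participants and the study clinician cannot realistically be masked to a conversation compared with usual care. The person asking the outcome questions can be, and the protocol does not provide for it. The engagement and conversation surveys are subjective and are given by voice, so an interviewer who knows the arm may prompt, pace or record answers differently. Deciding whether a chart entry counts as a new ACP conversation also leaves some room for judgement.

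A difference that arises this way is systematic, and a larger sample does not shrink it. Section 9 says that the trial's product is a preliminary effect size, and Section 1 says that the findings will support a larger multi-site trial. Assessor bias would therefore pass directly into the planning of that trial.

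**Working it through.** The plan gives no figure for assessor bias, so there is none to reproduce. The check sets the passages side by side and then shows how sensitive the comparison would be.

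**1. Is the RA role exposed to the arm?** Yes, at the initial visit. An RA who steps in once ED GOAL has been completed has reason to know that the participant received it, and nothing in the usual-care arm imitates it.

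**2. Is the follow-up assessor the same person, or told the arm?** The documents do not say. Section 6 uses one role title for both visits. Section 4 (Local Recruitment Procedures) shows that there is more than one RA: "Trained RAs will search through the medical records to find potential subjects". Neither separation nor identity is stated.

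**3. Does coaching reveal the arm before the one-month survey?** Not necessarily. It depends on what the participant reports at that visit, and the study clinician gives it. It could inform an RA before the 3- and 6-month surveys. It matters at one month only if the RA already knows who is eligible for coaching. The text does not say whether control participants are coached.

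**4. Is the EMR review masked?** No masking is stated. With the participant's permission, the study clinician also writes findings in Epic's ACP module (Section 6), so an abstractor with the whole chart may see the arm there.

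**5. How sensitive is the comparison?** Inputs:
- n = 60 per arm (Section 2, Section 9), or 60 × 0.90 = 54 after the 10% deaths that Section 9 expects.
- Two-sided alpha 0.05. Section 9 gives the threshold, and its power statement is two-sided.
- A survey SD of about 1.0 point, derived from Section 9, which equates a rise from 3.8 to 4.3 with an effect size of 0.50: 0.5 / 0.50 = 1.0. The SD itself is not stated.
- b, the differential assessor shift in SD units. The documents give no value, so the range below is assumed.

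With a true effect of zero and a normal two-sample comparison, SE = √(2/n), which is √(2/60) = 0.183 for 60 per arm and √(2/54) = 0.192 for 54.

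Rejection rate = [1 − Φ(1.96 − b/SE)] + Φ(−1.96 − b/SE).

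For b = 0.10 and n = 60: b/SE = 0.548, and the two tails are 7.9% + 0.6% = 8.5%. For b = 0.25: b/SE = 1.369, and the tails are 27.7% + less than 0.1% = 27.8%.

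| Assumed shift b (SD) | 60 per arm | 54 per arm |
|---|---|---|
| 0 | 5.0% | 5.0% |
| 0.05 | 5.9% | 5.8% |
| 0.10 | 8.5% | 8.1% |
| 0.20 | 19.5% | 18.0% |
| 0.25 | 27.8% | 25.5% |
| 0.30 | 37.6% | 34.4% |

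Whatever n is, the expected estimate moves by b itself.

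**The case against.** The strongest reply is that the documents are merely silent, and that silence in a pilot not powered to detect significant differences is a reporting gap. Several parts of this stand.

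- A reader might infer that the outcome assessor does know the arm, or that the workflow rules out masking. Neither is supported. There are several RAs, no passage assigns the same one to both visits, and the workflow allows masking without requiring it.
- A reader might infer that coaching unmasks the RA at one month. As step 3 shows, it need not.
- The EMR endpoint is not purely a judgement. Code status changes and advance directive forms leave less room for interpretation than conversation notes. Its standing as primary also differs between Section 6 and Section 9.
- Removing study-team entries from the abstractor's chart view would do more than mask. It would change what the endpoint counts, which is a separate decision.
- The assumed shift should not be expressed as a share of the planned effect of 0.25. Section 9 pairs that figure with Fisher's exact test, so it may be a difference in proportions rather than a standardized mean difference.
- The engagement surveys are validated self-report instruments answered by people who know their arm. Masking the RA does not remove that source of bias.

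The reply does not dispose of the point. Low power is no defence when the purpose is an effect-size estimate, because differential assessment biases the estimate at any sample size. The omission also concerns how the trial is run, since the plan can be followed to the letter with an assessor who knows every allocation.

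**Conclusion.** The point holds in this form: the protocol exposes the RA role to the arm at the initial visit, has an RA give the subjective one-month surveys at a contact shared with coaching, and states no masking of that RA or of the EMR abstractor. Avoidable interviewer and abstractor bias in the one-month comparison is therefore not guarded against.

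Its size cannot be derived from the documents. The false-positive rates of about 8.5% and 28% at 60 per arm rest on assumed shifts of 0.10 and 0.25 SD, no true effect and a normal approximation. They show sensitivity and do not predict what will happen. This is an inexpensive improvement to make before follow-up begins; it does not invalidate the design.

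**What to change.** Add protocol text stating who is masked and how:

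1. The 1-, 3- and 6-month surveys are given by an existing RA who took no part in that participant's initial visit and whose REDCap view hides the arm.
2. The full survey is completed and submitted before any coaching hand-over. The study clinician handles the hand-over, which may be at the same appointment.
3. EMR abstraction is done by an RA not told the arm, using fixed coding rules. Whether study-team entries count toward the endpoint is settled separately and in writing.
4. Any accidental unmasking is recorded.
5. Because participants stay unmasked, self-report bias is stated as a remaining limitation of the effect size carried to the future trial.

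The cost is protocol text, REDCap user rights and RA scheduling. Sample size, alpha and the intervention do not change. The downsides are less continuity between RA and participant, some scheduling effort, and imperfect masking, since some participants will reveal their arm and some charts will show it.
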